**Table 2-10 C-SSRS components**

Category number	C-SSRS category
Suicidal Ideation	
1	Wish to be dead
2	Non-specific active suicidal thoughts
3	Active suicidal ideation with any methods (not plan) without intent to act
4	Active suicidal ideation with some intent to act, without specific plan

Category number	C-SSRS category
5	Active suicidal ideation with specific plan and intent
Suicidal behavior	
6	Preparatory acts or behavior
7	Aborted attempt
8	Interrupted attempt
9	Actual attempt
10	Completed suicide
Self-injurious behavior, without suicidal intent	
11	Non-suicidal self-injurious behavior

#### 2.7.4.6 Amnesia/ memory gaps

For participants who have amnesia reported as AE after completing the memory assessment questions, the memory gap eCRF page will be filled.

A listing will be provided for participants with memory gaps by treatment arms.

## 2.8 Pharmacokinetic endpoints

### 2.8.1 Variables

Pharmacokinetic (PK) plasma samples will be collected from each study participant in accordance with the assessment schedule to determine the MIJ821 concentration. Only samples from participants treated with MIJ821 will be analyzed. Concentrations will be expressed in mass per volume units.

The following PK parameters will be determined after single s.c. injection using the actual recorded sampling times and non-compartmental method(s) with Phoenix WinNonlin (Version 8.0 or higher):

- primary PK parameters: AUClast, Tmax, and Cmax
- secondary PK parameters: if data permit, additional PK parameters will be estimated e.g. T1/2, AUCinf, AUC0-t (if needed, time range to be defined during PK analysis), CL/F, Vz/F (data not limited)

### 2.8.2 Descriptive analyses

In addition to the commonly used statistics, additional statistics will be used for summarizing the PK endpoints. The N values are defined as the number of participants with valid measures in each dose arms in the PK analysis set. The %CV (coefficient of variation percent) values will be summarized using the arithmetic mean calculated as '100\*(standard deviation / mean)' and the geometric mean calculated as 'sqrt (exp (variance for log transformed data)-1)\*100'.

All MIJ821 plasma concentrations and PK parameters including their descriptive statistics will be presented with three significant figures. The exception will be %CV values, which will be reported to one decimal place and N values, which will be reported as whole integers.

Concentrations below LLOQ will be treated as zero in summary statistics and for PK parameter calculations.

#### Concentrations

- will be listed by dose, subject, nominal sampling time and actual sampling time and containing information on body weight, age, gender, genotype classification
- will be graphically presented as concentration-time course per individuuum (individual plot per graph, linear-linear and log-linear plots)
- will be graphically presented as concentration-time course per dose as spaghetti plot (overlying individuuum courses, linear-linear and log-linear plots)

#### Summary statistics of concentrations by dose and nominal time

- will include mean (arithmetic and geometric), SD, CV (arithmetic and geometric), median, minimum, maximum, N values, and the frequency (n, %) of concentrations below the LLOQ. A geometric mean will not be reported if the dataset includes zero values.
- will be graphically presented as concentration-time courses of arithmetic means and nominal times (SD) by dose (overlying, linear-linear and log-linear plots)

#### PK parameters

- will be listed by dose and subject and containing information on body weight, age, gender, genotype classification

#### Summary statistics of PK parameters by dose

- will include mean (arithmetic and geometric), SD, CV (arithmetic and geometric), median, minimum, maximum, and N values. A geometric mean will not be reported if the dataset includes zero values. An exception to this is Tmax where median, minimum and maximum will be presented.

[REDACTED]

[REDACTED]

[REDACTED]

[REDACTED]

[REDACTED]

[REDACTED]

[REDACTED]

[REDACTED]

[REDACTED]

[REDACTED]

[REDACTED]

[REDACTED]

[REDACTED]

[REDACTED]

[REDACTED]

[REDACTED]

[REDACTED]

[figure not shown]
[REDACTED]

[figure not shown]
## 2.9 PD and PK/PD analyses

[figure not shown]
The exposure response relationship will be presented graphically for PK exposure parameters (e.g. Cmax and AUClast) and the change from baseline MADRS score derived at 24 h postdose and Day 8, Day 15, Day 22 and Day 29 during the follow-up.

[figure not shown]
Correlations will be assessed using statistical analysis methods (e.g. trendline analysis methods) and simple exposure response models (e.g. Sigmoid Emax models). Scatter plots of change from baseline of MADRS score (y-axis) versus PK exposure parameter (x-axis) will be provided by visit and the fitted lines and 90% pointwise confidence intervals from both the trendline analysis and Sigmoid Emax model will be added in the plots separately for each visit.

The hill parameter in the Sigmoid Emax models will be estimated if data allows. In case the model dose not converge, the Emax model with hill parameter equals 1 will be used. A table with estimated placebo effect and estimated parameters from the Sigmoid Emax models will be presented by visit.

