Data analysis	To assess the efficacy, change from baseline in the MADRS score at 24 hours after single s.c. injection will be analyzed using an analysis of covariance (ANCOVA) model with treatment as a group factor, class of antidepressant and baseline MADRS as a covariates, the Multiple Comparison Procedure - Modeling (MCP-Mod) methodology will be used to test the null hypothesis of a flat dose-response for the primary efficacy endpoint at a one sided significance level of 5% against the alternative hypothesis of a non-constant dose-response curve. If dose-response signal is detected, the MCP-Mod methodology, will also be employed to investigate the dose-response relationship.
Key words	Treatment-Resistant Depression; Major Depressive Episode; Major Depressive Disorder

1 Introduction

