6.2 Other treatment(s)

6.2.1 Concomitant therapy

All medications, procedures and significant non-drug therapies (including physical therapy and blood transfusions, SARS-CoV-2 vaccine) administered after the participant was enrolled into the study must be recorded in the concomitant medications/significant non-drug therapies CRF.

The investigator should instruct the participant to notify the study site about any new medications he/she takes after the participant is enrolled in the study. All medications, procedures and significant non-drug therapies administered after the participant is enrolled into the study must be recorded. The start and stop date and time of each medication use should be recorded as precisely as possible.

Each concomitant drug must be individually assessed against all exclusion criteria/prohibited medication.

All allowed concomitant baseline psychotropic medications used for treatment of depression must be documented as Standard of Care (SoC) and remain unchanged throughout the study. Any change in SoC after randomization (dose changing or starting new drugs) should be documented in medical records and reported in the eCRF.

Certain benzodiazepines, specifically lorazepam or alprazolam (as authorized by country), will be allowed for episodic or chronic use. These should not be taken within 12 hours before and within 4 hours after dosing unless it is used as rescue medication not to exceed 2 mg in a 24-hour period. Such lorazepam or alprazolam use will be documented as concomitant medication(s) and administration time should be documented in medical records and reported in the eCRF.

Any vaccinations should not be administered within 2 days prior to randomization.

For participants taking strong CYP2D6 inhibitors (e.g., berberine, bupropion, dacomitinib, fluoxetine, paroxetine, quinidine), the immediate time period after s.c. administration should be monitored with extra caution. All safety observations should be carefully observed for increased or unexpected frequency and severity.

Based on nonclinical information, MIJ821 is predicted to be eliminated predominately by oxidative metabolism via CYP2D6 (64% of elimination). Inhibition of the elimination pathways may lead to an increase of MIJ821 exposure. The following investigations have been executed to assess the potential drug-drug interaction on the major elimination pathway via CYP2D6:

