• The impact of strong CYP2D6 inhibitors (e.g., fluoxetine, paroxetine and bupropion) on the exposure of i.v. infused MIJ821 has been investigated in drug-drug interaction (DDI) simulations by means of the SimCYP® software. The simulated Cmax values were in

maximum 1.3-fold higher in the presence of fluoxetine or paroxetine and the AUC values in maximum 2-fold for all CYP2D6 genotypes (poor, extensive, or ultra-metabolizers). The resulting mean exposure values in the presence of strong CYP2D6 inhibitors are within the exposure range investigated in the FIH study after i.v. infusion (CMIJ821X2101, doses: 0.016, 0.048, 0.16, 0.24, 0.32 and 0.48 mg/kg). For the strong CYP2D6 inhibitor bupropion, no drug-drug interaction was estimated. Comparable impact of the MIJ821 exposure is expected after s.c. administration in the presence of strong CYP2D6 inhibitors since the i.v. and s.c. routes of administration are comparable in terms of circumventing the liver first-pass. Following s.c. administration of the highest dose (12 mg) in the s.c. SAD study with HVs (CMIJ821A02101), the exploratory mean AUClast and Cmax values are 257 h*ng/mL and 77.4 ng/mL, respectively, being comparable to the exposure values after i.v. infusion of 0.16 mg/kg MIJ821 in the FIH study (CMIJ821X2101). As discussed above, the mean exposure values after s.c. administration of the highest dose in this study (10 mg) are within the exposure range investigated in the FIH study in the presence of strong CYP2D6 inhibitors.

• Furthermore, in the PoC study (CMIJ821X2201, doses: 0.16 and 0.32 mg/kg), approximately 70% of participants received at least one CYP2D6 inhibitor (weak to strong CYP2D6 inhibitor or combinations of them). The Cmax values at both doses and the AUC values at 0.16 mg/kg do not exceed the exposure range determined in the FiH study.

Based on overall clinical experience (CMIJ821X2101, CMIJ821X2201), the totality of the safety data suggest that MIJ821 is generally safe and well tolerated and observed adverse events were transient. The risk of an overdose or unexpected AEs due to an exposure increase by CYP2D6 inhibition is considered to be low for the proposed MIJ821 doses being less or equal to 10 mg. In conclusion, CYP2D6 inhibitors are allowed as co-medications. Nevertheless, caution has to be taken when strong CYP2D6 inhibitors are administered.

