12.5.6 PK/PD relationships

The exposure response relationship will be presented graphically for PK exposure parameters (e.g. Cmax and AUClast) and the MADRS score change from baseline at 24 h after s.c. injection. Correlations will be assessed using statistical analysis methods (e.g. trendline analysis methods) or simple exposure response models (e.g. Emax models) if data allows. Details are described in the Statistical Analysis Plan.

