## 2.6 Analysis supporting secondary objective(s)

### 2.6.1 Efficacy endpoint(s)

#### 2.6.1.1 Duration of antidepressant effect of MIJ821

##### Change from baseline in the MADRS total score over time

Derivation of the MADRS total score is covered in [Section 2.5.1.1](#). The change from baseline in MADRS total score will be summarized for all collected data (including 4-hour post-dose) by visit/timepoint and by treatment arms. In case of unblinding, the MADRS scores collected after patient's unblinding will be excluded in all the analysis. A listing of MADRS total score for each participant at each visit will be provided by treatment arm.

The change from baseline in MADRS total score at follow-up visits on Day 1 4 h post-dose, Day 2, 8, 15, 22 and 29 will be analyzed using the mixed-effects model for repeated measures (MMRM). This model will include the fixed, categorical effects of treatment, time (i.e. analysis visits), baseline MADRS score, class of anti-depressant standard of care, treatment-by-time and baseline MADRS score-by-time interactions. [REDACTED]

A summary table with model estimated means and their differences of each MIJ821 doses vs. placebo, will be obtained at each visit/timepoint, along with the 90% CI for the difference. Model estimated treatment means in change from baseline in MADRS score ( $\pm$ SE) will be plotted over time/visit for each arm.

[REDACTED TABLE]

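### The visible exposure-response models in SAP 2.9 name no covariate, although the ANCOVA and MMRM adjust the same MADRS change for baseline MADRS and antidepressant class; adding both is a cheap improvement

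*SAP*

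**What the plan says.** **Exposure-response.** SAP 2.9 relates MADRS change to Cmax and AUClast at 24 hours and on Days 8, 15, 22 and 29: "Correlations will be assessed using statistical analysis methods (e.g. trendline analysis methods) and simple exposure response models (e.g. Sigmoid Emax models". Fits are shown by visit with 90% pointwise intervals. The Hill parameter falls back to 1 if the sigmoid model does not converge, and an estimated placebo effect is tabulated. Protocol 12.5.6 covers the 24-hour change only: "Correlations will be assessed using statistical analysis methods (e.g. trendline analysis methods) or simple exposure response models (e.g. Emax models) if data allows". Neither names a covariate.

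**Other analyses of the same outcome.** The ANCOVA in the protocol summary (Data analysis row) has "class of antidepressant and baseline MADRS as a covariates". The MMRM in SAP 2.6.1.1 has "baseline MADRS score, class of anti-depressant standard of care, treatment-by-time and baseline MADRS score-by-time interactions". Protocol 6.4.2 stratifies randomisation by antidepressant class.

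**Background drugs and exposure.** Protocol 6.2.1 says that "MIJ821 is predicted to be eliminated predominately by oxidative metabolism via CYP2D6 (64% of elimination". It reports simulated Cmax at "maximum 1.3-fold higher in the presence of fluoxetine or paroxetine and the AUC values in maximum 2-fold for all CYP2D6 genotypes", and adds: "For the strong CYP2D6 inhibitor bupropion, no drug-drug interaction was estimated". Inhibitors are allowed as co-medication. SAP 2.3.2 lists CYP2D6 phenotype among the baseline characteristics.

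**Use of the result.** Protocol 1.2 says that dose-response and exposure-response information will guide dose selection for confirmatory studies. Protocol 12.5.1 bases the target dose on the MCP-Mod dose-response curve.

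**The concern.** Two variables that the sponsor treats as worth adjusting for are absent from the visible plan for the one efficacy analysis whose regressor is not randomised. In the ANCOVA, randomised dose protects against confounding and the covariates mainly add precision. Exposure has that protection only for the part of its variation that comes from dose.

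Two things are at stake. If baseline MADRS predicts change, leaving it out widens the interval around the slope. If background drugs that raise exposure also shift MADRS change at 24 hours, the slope mixes that shift with the drug effect. Of the three SSRIs recommended in protocol Appendix 6, two (fluoxetine and paroxetine) are named as strong CYP2D6 inhibitors in 6.2.1. A link between class and exposure within a dose is therefore plausible.

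**Working it through.** **1. The plan's own figure.** None is stated for exposure-response. The 90% power in SAP 3 belongs to the MCP-Mod test. It cannot be reproduced, because the planned effect, SD and candidate curves are not in the public text. With six assumed sigmoid Emax shapes, 14 per arm and one-sided 0.05, it corresponds to a maximum standardised effect of about 1.05 (power 89% to 93% across shapes). It is plausible, but does not bear on this point.

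**2. Precision from baseline MADRS.** If baseline is unrelated to exposure and correlates with change at ρ, adding it lowers the slope's standard error by 1 − √(1 − ρ²). The documents give no ρ, so a range is shown.

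| assumed ρ | 0.1 | 0.2 | 0.3 | 0.4 | 0.5 |
|---|---|---|---|---|---|
| reduction in SE | 0.5% | 2.0% | 4.6% | 8.3% | 13.4% |

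**3. Inputs for the confounding check.**
- From the documents: 14 per arm; AUClast 257 h·ng/mL at 12 mg s.c. (protocol 6.2.1); a proof-of-concept effect of −8.25 points (protocol 1.1.3); a maximum 2-fold AUC rise.
- Assumed: dose-proportional AUC, giving 257 × 1/12, 4/12 and 10/12 = 21.4, 85.7 and 214.2; AUC CV 30%; residual SD 7.65; a linear slope of −8.25/214.2 = −0.0385 per unit; placebo at zero exposure; 10% to 40% of participants on an inhibitor; and an inhibitor effect γ on MADRS change of 0 to 3 points.

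**4. Formula check.** The bias in the unadjusted slope is γ × corr(A, I) × SD(I)/SD(A), where A is AUC and I is inhibitor use. Take 25% on inhibitors:
- SD(I) = √(0.25 × 0.75) = 0.433, and the simulated corr(A, I) is 0.279.
- Mean AUC is multiplied by 1.25, giving arm means of 0, 26.75, 107.1 and 267.75, with variance 10,889.
- Dose explains 70.2% of the AUC variance, so SD(A) = √(10,889/0.702) ≈ 124.6.
- For γ = 3 the bias is 3 × 0.279 × 0.433/124.6 = 0.0029, or 0.0029/0.0385 ≈ 7.5% of the slope. For γ = 1 it is about 2.5%.

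**5. Simulation (4,000 trials per scenario, 2-fold rise, ρ = 0.3).** Ratio of the mean unadjusted slope to the true slope:

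| on inhibitors | γ = 0 | γ = 1 | γ = 2 | γ = 3 |
|---|---|---|---|---|
| 10% | 0.998 | 0.988 | 0.967 | 0.960 |
| 25% | 1.001 | 0.976 | 0.963 | 0.923 |
| 40% | 0.999 | 0.975 | 0.950 | 0.928 |

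The bias is 0% to 8%. With γ = −3 the slope is overstated by 4% to 8%. With a 1.3-fold rise in 25% of participants the bias is 1% to 4% for γ of 1 to 3. Adjusting for inhibitor use brings the ratio to 0.99–1.01. One standard error of the slope is about 20% to 28% of the slope, so the bias stays below it.

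**6. If placebo is left out of the fit.** SAP 2.9 does not say whether placebo enters at zero exposure. In the three active arms alone, with γ = 3 and a 1.7- to 2-fold rise in 25% to 35%, the bias was 8% to 9% on a linear scale and about 13% on a log scale (SD 8, ρ = 0.4).

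**7. Cost.** Standard error as a share of the slope (25% on inhibitors, γ = 0):

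| ρ | unadjusted | + baseline | + baseline and inhibitor use |
|---|---|---|---|
| 0.1 | 0.219 | 0.220 | 0.229 |
| 0.3 | 0.223 | 0.215 | 0.225 |
| 0.5 | 0.223 | 0.196 | 0.204 |

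The inhibitor term costs about 4% to 5% here, which cancels the baseline gain at ρ = 0.3. In bounded Emax fits with baseline and class on E0 (600 trials per scenario), every fit succeeded. The standard error was about 1% larger at ρ = 0 and 3% to 9% smaller at ρ of 0.3 to 0.5.

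**The case against.** The strongest reply is that confounding is not shown. It needs background drugs to shift MADRS change at 24 hours, and no section says that they do. Participants have already failed at least two antidepressants, the current one must be at a stable dose for at least four weeks, and standard of care is to stay unchanged. The 2-fold AUC figure is a simulated i.v. maximum for two drugs, and for Cmax the maximum is 1.3-fold. Dose is randomised within class over a 10-fold range and dominates exposure. All of this stands. It is why the bias is stated as possible and small.

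Class is also an imperfect proxy for inhibition. Sertraline is in the SSRI class, bupropion is outside it, and fluoxetine in combination falls in the third stratum. Suppose inhibitors are used by 65% of SSRI and 30% of other or combination participants. Adjusting for class then moved an active-arm slope (on log(1 + exposure)) only from about −2.19 to −2.29, against a true −2.5, with an SE about 4% larger. This stands too. Class earns its place as the stratification factor already used in the other models; inhibitor use or phenotype is the better check on confounding.

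Three stronger readings are tempting. A reader might infer that the plan ignores the covariates, but the methods are given as examples and nearby SAP text is redacted, so only the visible silence can be reported. A reader might infer that baseline MADRS confounds the slope, but nothing links it to exposure, so it matters for precision only. A reader might infer that this slope sets the dose, but protocol 12.5.1 takes the target dose from MCP-Mod.

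What does not stand is that convergence problems rule out the adjustment: the Emax fits above all succeeded, though the sigmoid form with a free Hill parameter was not tested.

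**Conclusion.** The point holds as a cheap improvement. The visible plan gives no reason to treat this analysis differently from the ANCOVA and MMRM. The precision gain depends on a baseline-change correlation that the documents do not give, and it is worth having from about 0.3 upwards. The confounding figures rest on assumed inhibitor shares, an assumed effect on MADRS, dose-proportional AUC and a linear slope. They support saying that the slope may be modestly biased. They do not support saying that it is confounded, or that dose selection would be wrong.

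**What to change.** In SAP 2.9:
- Add baseline MADRS (centred) and antidepressant class as additive covariates on E0, that is, the intercept, in the trendline and the (sigmoid) Emax fits. Use the eCRF-based class that SAP 2.1.1.1 prescribes for analyses.
- Plot the fitted curves at mean baseline MADRS and keep the unadjusted scatter plots and fits.
- Add one sensitivity fit that replaces class with strong CYP2D6-inhibitor use or CYP2D6 phenotype.
- State whether placebo participants enter at zero exposure.

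The cost is a few lines of SAP text and three parameters per fit (one for baseline, two for the three-level class). The standard error may be about 1% to 5% wider if the covariates are not prognostic. The data are already collected through baseline MADRS, the concomitant-medication record and the phenotype classification.

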### **3 Sample size calculation**

With the randomization ratio 1:1:1:1, the sample size of 14 per arm (placebo; MIJ821 1 mg; MIJ821 4 mg; MIJ821 10 mg) will provide approximately 90% power to detect a dose-response signal (i.e. to reject the null hypothesis of a flat dose-response curve where all MIJ821 dose means are equal to the placebo mean) with respect to change from baseline in MADRS at 24 hours post-dose using MCP-Mod methodology at the one-sided alpha = 0.05 level.

The six candidate DR curves (6 Sigmoid Emax) for power calculation are defined in [Section 2.5.2](#).

### **4 Change to protocol specified analyses**

Not applicable.

## **5 Appendix**

### **5.1 Imputation rules**

#### **5.1.1 Study drug**

Not applicable.

#### **5.1.2 AE date imputation**

Missing or partial start/stop dates for AE will be listed as it is in the associated listings.

For analysis that needs to use the start date of an AE, e.g. in determination of whether an AE is treatment-emergent, the details will be provided in the programming dataset specification (PDS).

#### **5.1.3 Concomitant medication date imputation**

Missing or partial start/stop dates and time for concomitant medication will be listed as it is in the associated listings.

For analysis that needs the start date and time of concomitant medication, the details of date/time imputation will be provided in the programming dataset specification (PDS).

##### **5.1.3.1 Prior therapies date imputation**

For prior medications with a stop date prior to Day 1, the start date will be imputed as the earliest possible start date and the stop date as the latest possible stop date. More details will be covered in the PDS.

